5.9.2. Storage of Product

Study product supplies must be stored in compliance with the label requirements in a secure place with limited or controlled access.

6. STUDY ASSESSMENTS AND PROCEDURES

This section lists the procedures and parameters of each planned study assessment. The exact timing of each assessment is listed in the Schedule of Events section.

Adherence to the study design requirements, including all assessments and procedures are essential and required for study conduct.

6.1. Visit 1 - Screening Visit

6.1.1 Telephone Screening

Prior to the screening visit, telephone screening of interested subjects may be conducted using a telephone script. This will be conducted by the site recruitment staff or designee.

6.1.2. Informed Consent

The investigator, or designee, must obtain written (signed and dated by the subject) informed from each subject participating in this study after adequate explanation of

Document Name	pject CCI protocol		
Туре	Version	Document Identifier	Effective Date
eldo clinical doc	5.0; Most-Recent; Effective; CURRENT	090032d580cfe581	23-Feb-2017 14:35:47
Reason For Issue	Auto Issue		

the aims, methods, objectives, and potential hazards of the study. The investigator, or designee, must also explain to the subjects that they are completely free to refuse to enter the study or to withdraw from it any time. Appropriate forms for documenting written consent will be provided by the investigator or by GSKCH. The investigator, or designee, should sign and date the consent form to confirm that the consent process was completed correctly. The subject will be provided with a copy of their signed and dated consent form and any other written information which they should be instructed to retain.

If, during a subject's participation in the study, any new information becomes available that may affect the subject's willingness to participate in the study, each ongoing subject should receive a copy of this new information and be re-consented into the study. Subjects should be provided with a copy of the signed and dated amended consent form.

6.1.3. Demographics

The Investigator, or designee, will record each subject's year of birth, gender and race. In accordance with FDA guidelines (Guidance for Industry: Collection of Race and Ethnicity Data in Clinical Trials, 2005, FDA) the ethnicity of subjects will also be captured.

6.1.4. Medical History and Concomitant Medication

For each subject, the medical history will be taken and reviewed by the Investigator or medically qualified designee. Details of any relevant medical or surgical history, including allergies or drug sensitivity, will be recorded in the CRF. Any concomitant therapy taken in the 30 days prior to the Screening Visit and throughout the study will also be recorded in the CRF.

6.1.5. Dental History

The Investigator, or medically qualified designee, will take a dental history from each subject and recorded in the CRF. Dental history will include information of all prostheses in the mouth, maxillary and mandibulary, as well as information regarding the age of the dentures, and how long the subject has worn dentures. Documentation of prosthetic teeth material will also be recorded by the Investigator in the CRF.

6.1.6. Well-Made Denture Assessment

The examiner will examine each subject's denture in the maxilla and mandible (if present) to determine if he/she considers it to be well made i.e.:

Document Name	Project CC protocol		
Туре	Version	Document Identifier	Effective Date
eldo clinical doc	5.0; Most-Recent; Effective; CURRENT	090032d580cfe581	23-Feb-2017 14:35:47
Reason For Issue	Auto Issue		

- Denture(s) has adequate vertical dimension, freeway space, horizontal occlusal relationships and border extension
- Denture(s) has acceptable contour and finish
- Denture(s) has acceptable porosity, tissue surfaces, polished surfaces, color and thickness.

For each denture, maxillary and mandibular, if present, the examiner will identify from what material it is made and indicate acceptable or unacceptable on the CRF.

6.1.7. OST Examination – Edentulous

The OST Exam-Edentulous will include the maxillary mucogingival fold, maxillary edentulous gingival mucosa, maxillary hard palate, mandibular mucogingival fold, mandibular edentulous gingival mucosa (if applicable), gingival mucosa (if applicable), labial mucosa (including lips), buccal mucosa, tongue, sublingual area, soft palate, submandibular area, salivary glands, tonsilar and pharyngeal areas. Observations will be made of any erythema, desquamation and ulcerations, and other relevant clinical observations. The results of the examination will be recorded in the CRF as either normal or abnormal. The location and brief description of any abnormalities will also be recorded. Adverse events will be assessed from the first OST examination at screening.

A single examiner should complete this assessment for all the subjects. If this is not possible, then the same examiner should perform this procedure for the same subject for all the visits.

6.1.8. Denture Bearing Tissue Score

The denture bearing tissue score (Kapur 1967) will be assessed by the investigator and recorded for the maxillary denture only on the appropriate CRF. There are no eligibility requirements associated with this measure in this bite force trial.

* Note, for completeness, the entire index (for maxillary and mandibular arches) is presented below. Due to an inconsistency observed in the original printed publication, the two descriptors below marked by an asterisk (*) have been modified (by inverting their order) to better reflect the authors intent and align with the grading scale.

Document Name	Project CO protocol		
Туре	Version	Document Identifier	Effective Date
eldo clinical doc	5.0; Most-Recent; Effective; CURRENT	090032d580cfe581	23-Feb-2017 14:35:47
Reason For Issue	Auto Issue		

Ridge Shape (for both Maxillary and Mandibular)

- 1= Flat
- 2= V-shaped
- 3= Shaped between U and V
- 4= U shaped

Tissue Resiliency (for both Maxillary and Mandibular)

- 1= Flabby
- 2= Resilient
- 3= Firm

Location of Border Tissue Attachment

Maxillary Arch		Mand	ibular Arch
1=	Low	1=	High
2=	Medium	2=	Medium *
3=	High	3=	Low *

6.1.9. Kapur (Olshan Modification) Denture Retention & Stability Assessment

At the screening visit, the examiner will determine the subject's denture retention and stability score and it will be recorded in the CRF.

Retention Criteria

With gloved hands, the examiner will attempt to unseat the maxillary complete denture by applying an opposing vertical force at the canine/lateral incisor region of the denture. The examiner will score **retention** as 0 - 5 using the following criteria:

- 5= Excellent- denture offers excellent resistance to vertical pull and lateral force
- 4= Very Good- denture offers very good resistance to vertical pull and lateral force
- 3= Good- denture offers moderate resistance to vertical pull and lateral force
- 2= Fair- denture offers moderate resistance to vertical pull and little or no resistance to lateral forces
- 1= Poor- denture offers slight resistance to vertical pull and little or no resistance to lateral force

Document Name	Project or protocol		
Туре	Version	Document Identifier	Effective Date
eldo clinical doc	5.0; Most-Recent; Effective; CURRENT	090032d580cfe581	23-Feb-2017 14:35:47
Reason For Issue	Auto Issue		

0= No retention- when the denture is seated in place, it displaces itself

Stability Criteria

With gloved hands, the examiner will attempt to rock the seated dentures by placing alternate horizontal force at the cuspid and contralateral molar regions of the maxillary complete dentures. The examiner will score denture **stability** as 0-4 using the following criteria:

- 4= Excellent- when denture base offers no rocking on its supporting structures under pressure
- 3= Good- when denture base has very slight rocking on its supporting structures under pressure
- 2= Fair- when denture base has slight rocking on its supporting structures under pressure
- 1= Poor- when denture base has moderate rocking on its supporting structures under pressure
- 0= No stability- when denture base has extreme rocking under pressure

Following completion of informed consent (section 6.1.2), medical history/concomitant medication (section 6.1.4), dental history (section 6.1.5), well-made denture assessment (section 6.1.6), OST examination (section 6.1.7) and Kapur index/assessment (section 6.1.9), subject inclusion/exclusion will be determined as per the inclusion/exclusion criteria (section 4).

6.1.10. Denture cleansing

Dentures should be removed from the mouth by the subject. Denture cleansing should be performed by suitably qualified site staff. Enough denture cleansing paste will be applied to the supplied denture brush. Holding the upper (and lower where necessary) all surfaces of the dentures will be thoroughly cleaned to remove all traces of denture fixative, plaque and particulates/debris. The dentures will then be rinsed thoroughly with running water. Dentures should then be dried using clinical paper towels prior to denture adhesive application. Please note that the denture cleansing paste is to be used extra-orally and not for use in the mouth. Hands should be washed thoroughly following application and use of the denture cleansing paste.

Document Name	Project or protocol		
Туре	Version	Document Identifier	Effective Date
eldo clinical doc	5.0; Most-Recent; Effective; CURRENT	090032d580cfe581	23-Feb-2017 14:35:47
Reason For Issue	Auto Issue		

6.1.11. Mandibular Denture Stabilisation

Prior to all bite force measures, if deemed necessary at the discretion of the Investigator in order to ensure accuracy of bite force measures, any lower denture (partial or complete) will be fully stabilized by the investigator using the positive control denture adhesive (Super Poligrip® Free Adhesive Cream). This will be completed, when necessary, for all screening, practice, training and test bite force measurements.

6.1.12. Bite Force Measures prior to and at Screening

A bite force transducer system will be supplied by GSKCH and used to measure incisal bite force needed to dislodge the maxillary denture. The transducer system is composed of two plates embedded with a strain gauge that measures displacement of the upper denture during biting.

Each subject will have their bite force assessments with the same examiner. In this way inter-examiner variability will be minimized. Bite force data will be recorded on the appropriate CRF page.

6.1.13. Bite Force Calibration

The bite force device will be calibrated using appropriate software or through the application of incremental forces to the transducer by GSKCH's external vendor Specialty Measurements Incorporated (SMI), in agreement with GSK staff and the investigator prior to commencing the study. A Certificate of Calibration (which lasts for 12 months) will be provided before the start of the study and filed within the site's Regulatory Binder and the Study Master File.

6.1.14. Bite Force Measures at Screening

At Screening, subjects will have any denture adhesive on their denture removed. A member of site staff (trained in bite force procedures) will instruct the subjects in the execution of the bite force procedure participation. The subject will be instructed to sit and hold his/her head in a natural position so that the occlusal plane is parallel to the floor. The examiner will stand or sit in front of the subject holding the bite force transducer parallel to the floor at a comfortable level for the subject. In order to facilitate insertion the examiner may angle the bite force plates for certain subjects as necessary. The examiner will prevent cross contamination by placing a clean finger cot over the bite force plates for each subject in addition to a clean infection control sleeve over the transducer hand piece. The examiner will insert the bite force plates into the subject's mouth, which may be customized using impression material in

Document Name	Project Col protocol		
Туре	Version	Document Identifier	Effective Date
eldo clinical doc	5.0; Most-Recent; Effective; CURRENT	090032d580cfe581	23-Feb-2017 14:35:47
Reason For Issue	Auto Issue		

order to facilitate anterior denture tooth placement on the bite force transducer. The examiner will instruct the subject to swallow, and then ensure that the muscles of mastication are relaxed. The examiner will signal the subject to bite until he/she feels movement on the maxillary denture at which time he/she will be instructed to release the bite plate. If, in the opinion of the examiner, the subject will be unable to successfully complete the required bite force system training tasks, the subject will be withdrawn from the study.

During the Screening Visit, the examiner will record a triplicate bite force measurement at pre-treatment baseline without denture adhesive. These will be referred to as "training bites" on the CRF as the subject becomes accustomed to the equipment. Four (4) further bites will be made; 2 of these 4 'qualifying' bites must be reproducible (±2lb) for a subject to be eligible to the study. All 4 of the "qualifying" bites must be less than or equal to 9 pounds. These will form the subject eligibility/ adherence for continuation in the study.

6.2. Visits 2, 3, 4 & 5

6.2.1. OST Examination - Edentulous

Full OST edentulous assessments will be performed by the investigator twice during each of the Test Days; at pre-treatment baseline and also at the end of each of the Test/Treatment Visits. OST examinations will be performed as previously outlined in Section 6.1.7.

6.2.2. Denture Adhesive Application to Dentures

Prior to denture adhesive application, Denture Cleansing (Section 6.1.10) will be performed as previously described. Denture adhesive will be applied to the dentures by a suitably qualified member of site staff (blinded to the investigator collecting efficacy measures) as per the Denture Adhesive Application Instructions (Appendix V & VI). Upper dentures shall be weighed before and after adhesive application, and weights (including weight of adhesive used) recorded in the eCRF to ensure correct dose applied (1±0.05 grams). The specific tube used for denture adhesive application will be retained for use to assess product extrusion (Appendix III, question 6) to prevent the risk of cross-infection.

6.2.3. Bite Force Measures during Treatment Visits

Prior to Bite Force measures during each of the treatment visits, Denture Cleansing (Section 6.1.10) and Mandibular Denture Stabilisation (Section 6.1.11) will be performed as previously described.

Document Name	Project CC protocol	protocol		
Туре	Version	Document Identifier	Effective Date	
eldo clinical doc	5.0; Most-Recent; Effective; CURRENT	090032d580cfe581	23-Feb-2017 14:35:47	
Reason For Issue	Auto Issue			

On each treatment day, the examiner will record triplicate bite force measurements without denture adhesive. These three measurements will be referred to as "practice bites", where the goal is to have the subject re-familiarize themselves with the system. The 4th bite of the series will be captured as the Test Day pre-treatment baseline bite force. Test Day bite force readings must be within (±2 lb) for 1 of the 3 "practice bites" and the pre-treatment baseline bite. In addition, only subjects whose test day pre-treatment baseline bite force is less than or equal to 9 pounds will be eligible to proceed. If a subject does not meet these criteria at any test day visit they will be discontinued entirely from the study. Additional bite force measures will take place 0.5 (immediately prior to completion of product ooze questionnaire) followed by 1, 3, 6, 9 and 12 hours after application of each test adhesive (or no treatment as per the randomization schedule).

At each post-adhesive time-point, the subject will swallow and then bite on the transducer until the maxillary denture dislodges. No post adhesive application bite force measurements will be made earlier than the specified time and not later than 5 minutes after the specified time. Bite force data will be recorded on the appropriate CRF. Incidents will be assessed pre—and post—bite force recordings on each of the treatment days.

6.2.4. Subject Questionnaires

These questionnaires will only be completed by the subjects during treatment visits where subjects are assigned to adhesive.

A questionnaire pertaining to product ooze will be completed by the subjects immediately after the 0.5 hrs bite force measurement (Appendix II). Furthermore, a questionnaire regarding sensory attributes around flavour and texture will be completed immediately after completion of the 12 hrs bite force measurement whilst the upper denture is still retained in the mouth (Appendix III). Completion of this questionnaire will also involve the subject extruding some denture adhesive onto paper prior to answering the question regarding ease of product extrusion (question 6; Appendix III). A third and final denture removal questionnaire will be completed immediately following the 12 hrs bite force measurement, following completion of the sensory questionnaire and removal of the upper denture from the mouth by the subject (Appendix IV). This final "denture removal questionnaire" (Appendix IV) must be reviewed by Study Staff immediately following completion whilst the subject is still present, in order to ensure that any potential AEs that may be included in the free text (question 3; Appendix IV) are investigated by Study Staff and captured in the eCRF.

Document Name	Project CCI protocol		
Туре	Version	Document Identifier	Effective Date
eldo clinical doc	5.0; Most-Recent; Effective; CURRENT	090032d580cfe581	23-Feb-2017 14:35:47
Reason For Issue	Auto Issue		

All questionnaires will be completed by the subjects according to the study schedule (i.e. when undertaking the treatment, but not the no-treatment negative control study arms) in a quiet environment without external influence. Subjects will not be issued a questionnaire when completing the 'no adhesive' negative control treatment arm. The study Investigator(s) (in particular all site study staff involved in the collection of bite force and OST data) will remain blinded to the distribution and completion of all questionnaires. All questionnaire data will be captured in the eCRF, and will be monitored on site in order to ensure that all patient reported outcomes are captured in the database, paying particular attention to the free text about denture adhesive likes & dislikes (question 2; Appendix IV).

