8.4. Processing Patient Reported Outcomes

Patient reported outcome (PRO) data are collected directly from the subject PRO measures e.g. diary cards, questionnaires etc, and entered into the sponsor's clinical data management system (DMS) by the study site representative. In instances where the PRO data is entered into the DMS by GSKCH, the PROs will be anonymised, and forwarded to GSKCH for entry, as agreed and documented ahead of the study starting. PROs that are source will be retained by the investigator and certified copies will be sent to GSKCH.

In order to protect the privacy of subjects, no Personally Identifiable Information (PII) (including the subject's name or initials or birth date) is to be recorded on all PRO's that will be forwarded to GSKCH.

Document Name	Project CC protocol		
Туре	Version	Document Identifier	Effective Date
eldo clinical doc	5.0; Most-Recent; Effective; CURRENT	090032d580cfe581	23-Feb-2017 14:35:47
Reason For Issue	Auto Issue		

All PRO source data should be reviewed by the Study Staff/Study Monitor (as appropriate) in order to ensure that any potential AEs reported on these documents are represented in the DMS.

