12.4. Appendix IV - Denture Removal Questionnaire

Please note that this questionnaire is only completed for subjects on treatment visits when they have a denture adhesive applied and NOT on the no adhesive treatment visit.

To be completed by the subject immediately after denture removal.

Please mark/ tick only **ONE** response per question.

1. How EASY was it to REMOVE the denture from the	he mouth	ıth
---	----------	-----

Not at all easy	Slightly easy	Moderately easy	Very easy	Extremely easy
1	2	3	4	5

2. How EASY was it to REMOVE ANY RESIDUAL DENTURE ADHESIVE from the mouth?

Not at all easy	Slightly easy	Moderately easy	Very easy	Extremely easy
1	2	3	4	5

3. Please describe below what you LIKED or DISLIKED about the denture adhesive.

LIKED	

Document Name	Project CCI protocol				
Туре	Version	Document Identifier	Effective Date		
eldo clinical doc	5.0; Most-Recent; Effective; CURRENT	090032d580cfe581	23-Feb-2017 14:35:47		
Reason For Issue	Auto Issue				

DISLIKED	
DISLIKED	

Document Name	Project CCI protocol				
Туре	Version	Document Identifier	Effective Date		
eldo clinical doc	5.0; Most-Recent; Effective; CURRENT	090032d580cfe581	23-Feb-2017 14:35:47		
Reason For Issue	Auto Issue				

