8.3 Exploratory/Other Efficacy Analysis

Incisal Bite Force (lbs): Area over Baseline ($AOB_{0-0.5}$, AOB_{0-1} , AOB_{0-3} , AOB_{0-6} , AOB_{0-9})

Other efficacy bite-force efficacy variables analysed will be bite force AOBs over 0.5, 1, 3, 6 and 9 hours respectively. Each of these variables will be analysed using a similar ANCOVA model as described above for the primary efficacy variable.

From this model, treatment difference between each test adhesive versus Super Poligrip® Free, the treatment difference between each test adhesive versus no adhesive, 95% confidence intervals and p-values, will be provided. All significance tests will be conducted at the two sided 5% significance level.

Document Name	Statistical Analysis Plan for Study 206233.docx		
Туре	Version	Document Identifier	Effective Date
eldo clinical doc	1.0; CURRENT; Most-Recent; Effective	090032d580d17d34	27-Mar-2017 09:54:18
Reason For Issue	Auto Issue		

The data from the questionnaires and the denture adhesive weights will be listed and tabulated using descriptive statistics.

9 Safety Analysis

The safety profile of the study treatments will be assessed with respect to adverse events (AEs) and incidents. Oral soft tissue (OST) abnormalities are included as AEs if they appear or worsen after the initial assessment.

All safety data will be reported for the Safety population as per actual treatment received. All subjects screened will be included in the list of AEs.

All AEs will be reviewed by the Clinical Research Director or Designee prior to database freeze and will be coded using the Medical Dictionary for Regulatory Activities (MedDRA). During this review stage, AEs will be further categorized as oral or non-oral.

AEs will be regarded as treatment emergent if they occur on or after the date and time of the pre-treatment OST exam at the randomisation visit. All other AEs prior to this will be considered non-treatment emergent. AEs that occur during inter-test day washout are assigned to the last treatment received.

The following summary tables and listings will be presented by treatment group.

- Table of treatment emergent AEs by Oral/Non-Oral and Preferred Term
- Table of treatment emergent AEs by SOC and Preferred Term
- Table of Treatment emergent treatment related AEs by Oral/Non-Oral and Preferred Term
- Listing of all AEs (including Non-treatment emergent from All Subjects).

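### AEs found only through the free-text questionnaire can be recorded on adhesive visits but not on the no-adhesive visit, which tilts the descriptive adhesive versus No Adhesive AE contrast

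*Protocol*

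**What the plan says.** Protocol 6.2.4 (Subject Questionnaires) limits the forms to adhesive visits: "These questionnaires will only be completed by the subjects during treatment visits where subjects are assigned to adhesive". It then states the converse: "Subjects will not be issued a questionnaire when completing the 'no adhesive' negative control treatment arm". Appendix IV repeats the restriction for the denture removal form: "this questionnaire is only completed for subjects on treatment visits when they have a denture adhesive applied".

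Question 3 of that form is open text: "Please describe below what you LIKED or DISLIKED about the denture adhesive". Staff must check it while the subject is still on site. The stated purpose is as follows: "any potential AEs that may be included in the free text (question 3; Appendix IV) are investigated by Study Staff". Anything found is then entered in the eCRF. The visit lists in the synopsis and in Protocol 3.1 carry the same step. Protocol 8.4 extends the duty to all patient-reported source data, "in order to ensure that any potential AEs reported on these documents are represented in the DMS".

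For reporting, SAP Section 9 states: "The following summary tables and listings will be presented by treatment group". SAP Appendix 2 lists No Adhesive as the fourth treatment label for outputs. Neither document mentions the difference in AE detection between visits or plans to classify AEs by how they were found.

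**The concern.** In three of the four periods each subject is asked in writing what they disliked, and staff must look through the answer for AEs. In the fourth period nobody asks. If some complaints surface only in writing, they are counted under the adhesives and missed under No Adhesive, even when the true rates are equal.

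No Adhesive is the column that shows background complaints from wearing a denture and biting repeatedly over 12 hours. An excess in the adhesive columns over that background would mix any product effect with the extra prompt. The treatment-related table (9.4.3) may be the most exposed, because Question 3 asks about the adhesive itself and a complaint found there arrives already linked to the product. Protocol 3.4 says the trial is meant to inform whether the test adhesives progress, so an artefact against them would have some cost.

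**Working it through.** **Step 1: detection routes side by side.**

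| Route | Three adhesive visits | No-adhesive visit | Source |
|---|---|---|---|
| Standard AE question | Yes | Yes | Protocol 7.4 |
| Spontaneous report | Yes | Yes | Protocol 9.3.5 |
| OST examination before and after treatment | Yes | Yes | Protocol 6.2.1 |
| AE check before and after bite force | Yes | Yes | Protocol 3.1; Schedule of Events, footnote 7 |
| Question 3 free text screened for AEs | Yes | No | Protocol 6.2.4; Appendix IV |

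Only the last row differs. The other two subject questionnaires (Appendices II and III) are also adhesive-only, but they are tick-box forms, so Question 3 is the practical source. In the Protocol 3.1 visit list the check of the form comes before the final OST examination and the closing AE report. Many AEs written on the form could therefore also be found by a route that exists at every visit.

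**Step 2: which contrasts are affected.** The two test adhesives and Super Poligrip Free all have the route, so contrasts among them are balanced in this respect. Each adhesive versus No Adhesive is not. AOB analyses use no AE data. The plan's one design figure, about 81% power, concerns AOB and is not an input here.

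**Step 3: size.** The documents give no AE rate and no detection probability, so there is no planned figure to reproduce and every rate below is an assumption. The only document inputs are about 21 randomized and about 18 completing (Protocol 9.1).

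*Simple form.* Let q be the fraction of adhesive visits with an AE found only through the free text. The excess per adhesive column is 21 × q:

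- q = 2%: 21 × 0.02 = 0.4 subjects
- q = 5%: 21 × 0.05 = 1.1 subjects
- q = 10%: 21 × 0.10 = 2.1 subjects

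*Form with the common routes.* Let the true AE risk p be equal on every visit, let the common routes detect a fraction s₀, and let the free text recover a fraction e of what they miss. With N subjects:

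- No Adhesive: N·p·s₀
- Each adhesive: N·p·[s₀ + (1 − s₀)·e]
- Excess: N·p·(1 − s₀)·e
- Ratio: 1 + (1 − s₀)·e / s₀, which does not depend on N or p

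The ranges used were N = 18 to 21, p = 5% to 20%, s₀ = 50% to 90% and e = 0 to 50%. Selected results:

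| N | p | s₀ | e | Adhesive | No Adhesive | Excess | Ratio |
|---|---|---|---|---|---|---|---|
| 18 | 5% | 90% | 25% | 0.83 | 0.81 | 0.02 | 1.03 |
| 21 | 20% | 90% | 50% | 3.99 | 3.78 | 0.21 | 1.06 |
| 21 | 20% | 70% | 50% | 3.57 | 2.94 | 0.63 | 1.21 |
| 21 | 20% | 50% | 50% | 3.15 | 2.10 | 1.05 | 1.50 |
| any | any | any | 0 | equal | equal | 0 | 1.00 |

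The two forms agree, because q = p·(1 − s₀)·e. The largest value in the range is 0.20 × 0.50 × 0.50 = 5%, which gives 21 × 0.05 = 1.05. An excess of two subjects needs q = 10%, twice that maximum.

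**The case against.** The case against has several parts, and much of it stands.

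- **No Adhesive is not the only reference.** A reader might infer that the new formulations can be judged only against it. Super Poligrip Free is a marketed positive control (Protocol 3.4) with the same questionnaire, so test versus marketed adhesive is balanced for this route.
- **AE collection on the no-adhesive visit is not thin.** A reader might infer that AEs there are largely missed. Four of the five routes in the table operate at that visit, and subjects remain on site all day (Protocol 3.2).
- **Safety is descriptive.** It is not among the listed objectives in Protocol Section 2 or SAP Section 2, and no inferential AE analysis is planned. This limits the consequence without removing it: with no test, readers judge the raw columns directly.
- **The sources are not wholly inseparable.** SAP Listing 2.2 gives the Question 3 verbatims and Table 9.4.4 lists all AEs. An AE with no matching text did not come from Question 3. Whether the AE eCRF page already records a source is unknown, because the page is not in the documents.
- **The No Adhesive column is an inference.** The AE table shells are sponsor standards and are not shown. The inference is strong, since AEs can occur in that period and the tables are by treatment group.
- **A question about an adhesive does not apply when none is used, and screening patient-reported text for AEs is a proper duty.** Both are true. A dislike of taste is also not in itself an AE. The point concerns how the counts are shown, not whether the screening should happen.

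What survives is that the routes differ between visits, the direction is predictable, and no planned table isolates the effect.

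**Conclusion.** The point holds in a limited form. The no-adhesive period lacks one AE detection route that the three adhesive periods have, so AEs found only through that route tend to raise adhesive counts in the descriptive tables. Nothing else is affected.

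The size cannot be derived from the documents and is probably small. Under the stated assumptions it is roughly 0 to 1 event per adhesive column, and about 2 only under the more extreme assumption q = 10%. It is zero if the free text reveals nothing that the common routes miss. A reader might infer that this route could account for the whole visible difference between adhesive and No Adhesive. The documents do not support that, because they contain no rate from which to argue it. With about 21 subjects per column, one event could still be noticeable. That justifies a cheap improvement but is no threat to the trial's conclusions.

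**What to change.** Keep the screening of Question 3. Add the following.

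1. **Identify questionnaire-only AEs** in one of two ways. (a) Use an eCRF field completed by non-examiner staff, with access restricted under the provision in Protocol 5.8.2. (b) Derive it at the AE review before database freeze (SAP Section 9) by matching AEs to the Question 3 verbatims planned for Listing 2.2, under a rule fixed before unblinding.
2. **In SAP Section 9, repeat Tables 9.4.1 and 9.4.3 excluding questionnaire-only AEs.** Matching alone would also flag AEs that another route found, so under (b) the repeat tables may over-correct. The full and reduced tables then bracket the answer.
3. **Footnote the AE tables** to say that No Adhesive had no questionnaire route.

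The cost is one restricted field or a short matching step, two extra tables and a footnote. There is also a blinding risk. A source value naming the questionnaire, or the mere existence of a verbatim, reveals an adhesive visit. Protocol 6.2.4 keeps investigators blind to who receives questionnaires, while Protocol 7.3 and 7.4 have the investigator assess causality and review AEs. The field or the matching must therefore stay out of their view. Sample size, efficacy analyses and clinical management do not change.
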